## Relapse

Relapses are divided into major and minor. Relapses described without major/minor distinction include both types.

(1) Major relapse

Relapses that investigators decide that administration of prednisolone of more than 20 mg/day, an escalation dose of immunosuppressive agent, and/or treatment with other additional immunosuppressive agent are necessary, due to the new emergence or recurrence of BVAS ver3 items which indicate severe condition.

## (2) Minor relapse

New emergence or recurrence not meeting criteria for major relapses as assessed with BVAS ver3

## End-stage renal disease (ESRD)

Dialysis for 6 weeks or more is required, and there is no chance of recovery.

## **B** cell depletion

B cells in the peripheral blood are below the site's detection limit with flow cytometry.

## **B** cell recovery

B cells in the peripheral blood return to a level detectable with flow cytometry.

#### **1. Introduction**

## 1.1 Background of disease being studied

Antineutrophil cytoplasmic antibodies (ANCA)-associated vasculitis is a disease that is characterized by small vessel vasculitis and the presence of ANCA, and composed of microscopic polyangiitis (MPA), granulomatosis with polyangiitis (GPA; previously known as Wegener's granulomatosis), and eosinophilic granulomatosis with polyangiitis (previously known as Churg-Strauss syndrome). Life and renal prognosis are often poor in patients with ANCA-associated vasculitis, with five-year survival rate of approximately 75%, and of those, approximately 20% patients reportedly experience progression to end-stage renal disease (ESRD) [1].

#### 1.2 Standard therapy for disease being studied

The concomitant use of high-dose glucocorticoids and cyclophosphamide pulse therapy (IV-CY), which is a current standard remission induction treatment, has achieved a high remission rate of 80-90% [2-4]. However, this therapy is associated with a variety of side effects, particularly those attributable to high-dose glucocorticoids, including infections, osteoporosis/aseptic necrosis, hypertension/diabetes/dyslipidemia, cataract/glaucoma, gastric/duodenal ulcer, muscle weakness, menstrual disorder, steroid psychosis, insomnia, and moon-shaped face. Among these side effects, infections are strongly associated with deaths of patients with ANCA-associated vasculitis. In Japan, MPA, which frequently occurs most often in the elderly, account for the majority of ANCA-associated vasculitis, resulting in high mortality from infections compared to other countries, which accounts for approximately half of deaths [13]. Moreover, side effects that are not related to death also affect decreased patients' quality of life and growth in medical costs. Therefore, a new standard treatment with reduced side effects is awaited to be developed.

## 1.3 Background of this study

## **1.3.1 B cell-targeted therapy**

For treatment of ANCA-associated vasculitis, rituximab, an anti-CD20 monoclonal antibody that specifically depletes B cells, has been investigated in other countries for following reasons; (1) infiltration of B cells are found in inflammatory foci, (2) B cell activation is associated with the disease activity, and (3) cyclophosphamide, an immunosuppressive agent which is relatively specific to B cells, shows reasonable efficacy [5-6]. In two clinical trials published in 2010; RAVE trial (the United States) and RITUXVAS trial (Europe); the concomitant treatment of high-dose glucocorticoids and rituximab showed a remission induction rate equivalent to the combination of high-dose glucocorticoids and IV-CY in patients with new-onset ANCA-associated vasculitis [7-8]. The analysis of the relapsing cases in the RAVE trial

indicated that rituximab showed superior remission induction rate compared with IV-CY. As opposed to the initial expectation, that is, the rituximab group will show better safety results, the combination of high-dose glucocorticoids and rituximab was comparable with the combination of high-dose glucocorticoids and IV-CY also in terms of safety. For this reason, the indication of rituximab as remission induction treatment is currently limited to use for patients with relapses or those for whom the use of cyclophosphamide is undesirable. Two hypotheses may explain why the two regimens were comparable in safety in RAVE and RITUXVAS trials; ① rituximab and cyclophosphamide have equivalent risks, and ② statistical differences between the two groups were difficult to detect because high-dose glucocorticoids are associated with a majority of side effects in both groups. Given general perception of rituximab with high safety standards (except at the initiation of administration) based on previous reports [9-10], the hypothesis ② may be more likely to be true, and thus the glucocorticoid dose reduction is essential to improve safety.

## 1.3.2 Glucocorticoid dose reduction

RAVE and RITUXVAS trials suggested that the glucocorticoid dose reduction is required to develop a new treatment to reduce infection and other side effects. For immunosuppressive agents other than rituximab, previous studies have shown that the glucocorticoid dose reduction is associated with a reduced remission rate and an increased relapse rate [11-12], suggesting that the concomitant use with low-dose glucocorticoids is difficult. However, the efficacy of rituximab has not been examined in combination with low-dose glucocorticoids. As mechanism of action of rituximab on ANCA-associated vasculitis is substantially different from mechanisms of conventional immunosuppressive agents, rituximab is considered a valid option to achieve the glucocorticoid dose reduction in remission induction treatment. In fact, Smith et al. have reported that their observational study showed good remission re-induction rates (93-96%) with the concomitant use of rituximab and low-dose glucocorticoids in ANCA-associated vasculitis patients with major relapses [14].

## 1.3.3 Background of this study plan

In Japan, a public knowledge-based application was approved in June 2013 on the basis of results of RAVE and RITUXVAS trials, and insurance coverage of rituximab for MPA and GPA was approved. In addition, academic societies (Japan College of Rheumatology and Japanese Society of Nephrology) and the intractable vasculitis study group of the Ministry of Health, Labour and Welfare have released the joint statement on the use of RITUXAN for ANCA-associated vasculitis, in which the actual indications are specifically restricted as it should be considered "only when existing treatments, cyclophosphamide, produce insufficient effects, existing treatments are contraindicated, or in the patient have multiple

relapses." These indications were based on clinical trials conducted in other countries, and are largely similar to the indications in other countries. Therefore, although the use of RITUXAN for new-onset ANCA-associated vasculitis is within the insurance coverage, its use in daily medical practice is limited by relevant academic societies.

The objective of the present study is to verify whether rituximab can reduce a total amount of glucocorticoid dose while maintaining the remission induction rate in remission induction treatment for ANCA-associated vasculitis. By providing high-quality evidence, we hope that the current treatment guidelines developed by the Ministry of Health, Labour and Welfare study group will be revised, and ultimately, low-dose glucocorticoid therapy combined with rituximab can be used in daily medical practice.

## 2. Objectives

The objective is to verify whether rituximab can reduce a total amount of glucocorticoid dose in remission induction treatment of patients with new-onset ANCA-associated vasculitis. More specifically, this study aims to demonstrate the non-inferiority of concomitant use of low-dose glucocorticoid and rituximab compared to concomitant use of high-dose glucocorticoid and rituximab in terms of the efficacy in remission induction treatment of patients with new-onset ANCA-associated vasculitis.

## 2.1 Primary endpoint

## [Efficacy]

The proportion of participants who achieved remission at 6 months

## 2.2 Secondary endpoints

[Efficacy]

Time required to achieve remission

Overall survival period, relapse-free interval, time to ESRD, time to occurrence of the first serious adverse event

The proportion of death, relapse, ESRD, and patients with serious adverse events; and proportion of composite outcomes thereof (at 6 and 24 months; \*at 6 months, proportions of death, ESRD, and serious adverse events only)

Proportions of major and minor relapses

Assessment of disease activity using Birmingham Vasculitis Activity Score (BVAS) ver3

Assessment of irreversible damage using Vasculitis Damage Index (VDI) [19]

Evaluation of health-related QOL using SF-36

- 17 -

General assessment of patients using visualized analogue scale (VAS)

Cumulative dose of glucocorticoid

[Safety]

The number of adverse events and serious adverse events and proportion of patients with adverse events and serious adverse events

Proportions of new-onset diabetes, hypertension, and dyslipidemia requiring treatment

The proportion of sleep disorder requiring treatment

The proportion of pathological fractures and bone density of the lumbar spine

The number of infections and proportion of patients with infections that required intravenous or oral administration of antibiotics

[Exploratory]

Immunoglobulin concentration

Whole blood B cell count

Changes in MPO-/PR3-ANCA values associated with treatment, treatment responses, and relapses

## 3. Study Design

This is an open-label, randomized trial comparing two arms that undergo remission induction treatment with rituximab + low-dose glucocorticoids or rituximab + high-dose glucocorticoids. After the trial, patients in remission proceed promptly to maintenance treatment.

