## <Glucocorticoids>

Oral Predonine® is used in principle (the same amount of water-soluble Predonine® may be given via intravenous infusion only when oral administration is difficult). Doses and tapering schedules for high- and low-dose groups are described as follows. The dose for the high-dose group is identical to that in the conventional standard treatment. Only in cases in which BVAS does not reach 0, or CRP and ANCA values are not normalized, the principal investigator/co-investigator can postpone the initiation of the prednisolone discontinuation step (5mg/body/day to drug off in 14 weeks) in the low-dose glucocorticoid regimen. Once the step has been initiated, prednisolone should be discontinued 14 weeks after the initiation of the step.

weeks	Low-dose group	High-dose group
1-2	0.5mg/kg/day	1.0mg/kg/day
3-4	0.25mg/kg/day	0.8mg/kg/day

5-6	7.5mg/body/day	0.7mg/kg/day
7-8	5mg/body/day	0.5mg/kg/day
9-10	4mg/body/day	0.4mg/kg/day
11-12	3mg/body/day	0.35mg/kg/day
13-16	2mg/body/day	15mg/body/day
17-20	1mg/body/day	12.5mg/body/day
21-24	0mg/body/day	10mg/body/day

Thereafter, both groups receive the remission maintenance therapy with 1g of rituximab once every six months (at 6, 12, and 18 months). However, if it is difficult to administer a dose of 1 g/body in a single day, it can be given as two doses of 0.5 g/body (the second dose should be administered within two weeks after the first dose). In such a case, the first dose should be given at 6, 12, and 18 months, and the second dose should be given within two weeks after the first dose. The glucocorticoid tapering regimen in the maintenance treatment phase is left to the discretion of the primary investigator or co-investigators in the high-dose group.

 $\langle\!\langle Criteria \text{ for terminating the study} - \text{stopping rules} \rangle\!\rangle$ 

The primary investigator or co-investigators discontinues the study when any of the following criteria are met.

- (1) When an adverse event which falls under the dose reduction criteria occurred even after reducing the dose of the investigational agent to the minimum level, and the principal investigator or co-investigators find discontinuation necessary
- (2) When an adverse event occurs and makes continuation of administration of the investigational agent difficult, and the principal investigator or co-investigators find discontinuation necessary
- (3) When the patient requested discontinuation

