## 6.3 Maintenance treatment

For remission maintenance treatment during the post-treatment observation period, 1 g/body of rituximab will be administered every 6 months (6, 12, and 18 months). However, if it is difficult to administer a dose of 1 g/body in a single day, it can be administered as two doses of 0.5 g/body (the second dose is

administered within two weeks after the first infusion). In such a case, the first dose should be given at 6, 12, and 18 months, and the second dose should be given within two weeks after the first dose. The rituximab infusion can be started at a rate of 100 mg/hour, and the rate can be increased by 100 mg/hour every 30 minutes, up to 400 mg/hour. The choice of the premedication method is left to each study site. The glucocorticoid tapering regimen is left to the discretion of the principal investigator or co-investigators with no specific restrictions in the high-dose group.

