## [Rationale]

The results of previous clinical trials (RAVE and RITUXVAS trials) have suggested that the relapse rate is higher with only one course of rituximab treatment, resulting in requiring some form of remission maintenance treatment. In the Cambridge University cohort, which is one of the largest cohort of ANCA-associated vasculitis patients treated with rituximab, remission maintenance treatment with administration of 1 g/body rituximab every 6 months has been demonstrated to be effective in those who accomplished remission introduction with rituximab combination therapy, although the results have not validated by.

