#### [Rationale]

To demonstrate the non-inferiority in remission induction rate, the necessary number of cases calculated with the following conditions is 63 in each arm:

 $\alpha = 0.025$  (one-tailed),  $1 - \beta = 0.8$ 

(1)Remission induction rate with rituximab + high-dose glucocorticoids = 0.80

(2)Remission induction rate with rituximab + low-dose glucocorticoids = 0.80

Non-inferiority margin=-0.2

Allocation ratio, 1:1.

With a predicted withdrawal rate of 10%, the target sample size was set as 70 in each arm, a total of 140 cases. The induction rates (1) and (2) are based on RITUXVAS study [8] and the Cambridge University cohort, respectively [14].

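### Section 3 limits maintenance to patients in remission, while the synopsis and section 6.3 schedule it without that condition, so handling of month-6 non-remitters is not fixed

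*Protocol*

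**What the plan says.** Section 3 (Study Design) describes what follows induction: "After the trial, patients in remission proceed promptly to maintenance treatment". This names patients in remission only and puts maintenance outside the trial.

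The synopsis, after the 24-week glucocorticoid table, says: "Thereafter, both groups receive the remission maintenance therapy with 1g of rituximab once every six months (at 6, 12, and 18 months"). Section 6.3 likewise says that "1 g/body of rituximab will be administered every 6 months (6, 12, and 18 months"). Neither sentence makes the dose conditional on remission. Both call the treatment remission maintenance, and the rationale under section 6.3 cites evidence of benefit "in those who accomplished remission introduction with rituximab combination therapy".

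Other sections place this dosing inside the study. Section 3 gives a study duration of 24 months, section 7.2 runs the maintenance period from month 6 to month 18 with scheduled visits, and section 10.5 plans an analysis of the maintenance phase at 24 months.

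On timing, section 7.2 sets the month-6 visit at day 180 ± 15. The first maintenance dose is due at 6 months, with no window of its own.

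**The concern.** A site with a patient not in remission at month 6 finds one sentence that implies maintenance is not for that patient and two that schedule it regardless. The stopping rules in section 6.4 do not settle the matter. None of them mentions failure to reach remission, and several leave continuation to the investigator's judgement.

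Sections 9.2 and 10.5.2 evaluate death, relapse, ESRD, serious adverse events, their composite, VDI, SF-36 and infections at 24 months. The trial is open-label, so a site that decides case by case knows the patient's arm. If decisions about further rituximab went differently in the two arms, those 24-month comparisons would carry a treatment difference that the protocol did not intend.

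The shared month-6 time point raises a smaller question. If BVAS were scored after the first maintenance infusion, remission at 6 months would not be purely an induction result.

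**Working it through.** **Planning figures (section 10.2).** Inputs: "Remission induction rate with rituximab + high-dose glucocorticoids = 0.80"; "Remission induction rate with rituximab + low-dose glucocorticoids = 0.80"; "Non-inferiority margin=-0.2"; one-sided α 0.025; power 0.80; allocation 1:1; 10% withdrawal.

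n per arm = (1.960 + 0.842)² × (0.8×0.2 + 0.8×0.2) / 0.2² = 7.85 × 0.32 / 0.04 = 62.8, so 63. Then 63 / 0.9 = 70 per arm, 140 in total. The plan's figures reproduce and are not in dispute; they serve here only to size the affected group.

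**Patients without a fixed rule.** Non-remission at the planned rate is 1 − 0.80 = 0.20.
- As randomised: 0.20 × 70 = 14 per arm, 28 of 140.
- After 10% withdrawal: 0.20 × 126 = 25.2, about 25 of 126.
- Over an assumed 10% to 30% non-remission: 14 to 42 of 140.

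**Possible effect on a 24-month proportion.** The documents give no event risks for non-remitters, so the following rests on assumption. Let s be the non-remission proportion in an arm, f the fraction of those patients handled under the restrictive reading, and x the change in their 24-month event risk from withholding rather than giving maintenance, taken as equal in both arms.
- Shift in one arm = s × f × x.
- Shift in the between-arm difference = x × (s_low × f_low − s_high × f_high).

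With s = 0.20, f = 1 and an assumed x of 10 to 50 points, the one-arm shift is 0.20 × 0.10 = 0.02 to 0.20 × 0.50 = 0.10, that is 2 to 10 points. Over s = 0.10 to 0.30 it is 1 to 15 points. If s and f are equal in both arms, the between-arm shift is zero. It reaches the one-arm figure only in the extreme case where one arm follows one reading throughout and the other arm follows the other.

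**Order at month 6.** The visit window is day 165 to day 195. The taper covers 24 × 7 = 168 days, and the synopsis introduces maintenance as following it.
- Infusion on day 180, visit on day 195: assessment 15 days after infusion.
- Infusion on day 169, the first day after the taper, visit on day 195: 26 days.

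Assessment after infusion is therefore possible. One patient reclassified in one arm would move the primary risk difference by 1/70 = 1.4 to 1/63 = 1.6 points, against a 20-point margin.

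**The case against.** The strongest reply is that the texts can be read together. Each dosing text calls the treatment remission maintenance, section 3 speaks of patients in remission, and the cited evidence is in remitters. The words about both groups in the synopsis most naturally mean both arms, not every patient whatever the response. This has force. A reader might infer a flat contradiction, with one text ordering the dose for non-remitters and another forbidding it; no text does either explicitly. But the compatible reading still supplies no rule for non-remitters, and the unconditional schedule stays on the page.

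The reference to maintenance after the trial is probably loose wording for after induction. That stands, since the visit schedule makes clear that the doses fall within the study. It still needs correcting.

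On timing, the schedule in section 23.1 appears to list month 6 under induction, although the extracted table is broken, and the synopsis places maintenance after the taper. Assessment first is the natural order. A reader might infer a gap of up to 30 days by applying the whole visit window to the infusion. The documents do not support this: the infusion has no stated window, and day 165 lies inside the taper.

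It is also fair that the 24-month outcomes are secondary, and that they do not isolate the induction dose in any case, because glucocorticoid tapering during maintenance is left to discretion in the high-dose group. Nothing in the documents shows that sites would resolve the ambiguity differently by arm.

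**Conclusion.** The point holds as an unreconciled treatment rule. Section 3 conditions maintenance on remission, the synopsis and section 6.3 do not, and no section settles what non-remitters at month 6 receive. At the planned rate this leaves about 14 of 70 patients per arm, or about 25 of 126 in total after withdrawal, without a fixed rule.

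The consequence is for the secondary 24-month comparisons, and only if non-remission rates or the reading followed differ between arms. The 2-to-10-point one-arm shift depends entirely on the assumed risk change; it illustrates scale and does not estimate bias.

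Two stronger inferences are not supported. One is that each non-remitter receives either none or all 3 g of maintenance rituximab. That is the extreme contrast, since patients may remit later or discontinue. The other is that the primary result is biased. Both arms have the same maintenance schedule, the layout points to assessment first, and no effect on the primary comparison is shown. The missing order at month 6 is a minor, separate point that concerns the month-6 measures and does not bear on who receives maintenance.

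**What to change.** Reconcile section 3, section 6.3 and the synopsis into one rule on who proceeds to maintenance, covering patients not in remission at month 6 and applied identically in both arms. The choice of rule is for the sponsor. Correct the wording in section 3 that places maintenance after the trial.

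In section 7.2 and the schedule in section 23.1, require the month-6 BVAS and prednisolone dose, the two components of the remission definition, to be recorded before any month-6 maintenance infusion.

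The cost is a short protocol modification and a visit-order instruction to sites, with no additional patients, visits or tests. The sponsor would decide which category of change under section 15.4.1 applies.

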## Rationale for study design

This study is a multicenter, open-label, randomized controlled trial. To verify whether concomitant use of rituximab allows to reduce the glucocorticoid dose in remission induction treatment, the efficacy and safety of the remission induction treatment with rituximab + low-dose glucocorticoids are assessed using the remission induction treatment with rituximab + high-dose glucocorticoids as a control regimen. To test the hypothesis that the dose reduction of glucocorticoids is possible, this study aims to demonstrate the non-inferiority of the low-dose glucocorticoids group in efficacy.

It should be noted that the rituximab + high-dose glucocorticoids regimen to be used for the control group has been demonstrated to have the efficacy and safety equivalent to current standard regimen of cyclophosphamide + high-dose glucocorticoids by the results of previous clinical trials.

The study duration of 24 months and the primary endpoint of the remission induction rate at 6 months are the most widely used efficacy indices in clinical trials of remission induction treatments for vasculitis.

## 3.1 Target sample size and study period

Target sample size: 140 subjects

## [Rationale]

To demonstrate the non-inferiority in remission induction rate, the necessary number of study subjects calculated with the following conditions is 63 in each arm:

 $\alpha = 0.025, 1 - \beta = 0.8$ 

(1) Remission induction rate with rituximab + high-dose glucocorticoids = 0.80

(2) Remission induction rate with rituximab + low-dose glucocorticoids = 0.80

Non-inferiority margin = -0.2

Ratio 1:1.

With a predicted withdrawal rate of 10%, the target sample size was set as 70 subjects in each arm, a total of 140 subjects. The induction rates (1) and (2) are based on RITUXVAS study [8] and the Cambridge University cohort, respectively [14]. The non-inferiority margin was set in reference to the margin used in RAVE study, which was a non-inferiority study of rituximab [7].

Study period: October 1, 2014 – September 30, 2021

Patient enrollment period: October 1, 2014 - September 30, 2019

